3 DATA COLLECTION

Subjects will be followed per the hospital standard of care. Assessments collected in this registry are considered standard of care at most institutions. Please refer to Section 7 for the Visit Schedule.

3.1 Database

The data will be collected via an electronic data capture system (EDC). This database is maintained and administered by Abbott. Users will have unique usernames and passwords, and the user list will be maintained by a Sponsor's administrator for all study personnel.

3.2 Pre-implant Demographics and Profile

The standard demographics of age, gender, and subject-described ethnicity will be recorded. Heart failure etiology, duration, and standard prognostic factors will be collected along with hemodynamic, laboratory and echocardiographic parameters closest to the time of implant. Co-morbidities and previous cardiovascular medical history will be also included. The subjects functional and clinical status will be assessed by NYHA classification, INTERMACS Subject Profile and the 6 minute walk test. The subject will also be asked to complete the quality of life assessment.

3.3 Implant

The elements which characterize the HM3 device and describe the implant procedure will be recorded in the Registry database. Note that the implant form that is provided in the pump packaging should be completed following usual commercial device reporting procedures.

3.4 Post-Implant Follow-up

Refer to Section 7.0 for the visit schedule. Any subject related events (adverse events, reoperations, rehospitalizations, outcomes) should be reported as they occur. The date of discharge will be collected. The six minute walk and quality of life assessment will be administered at aseline and every follow-up as of 6 months visit.

3.4.1 Adverse Events (AE)

Adverse Events should be reported in the Registry database as they occur. The INTERMACS adverse event definitions will be used and can be found in Appendix 1.

Note that the usual commercial device reporting procedures should be followed for any non-adverse events device malfunctions and product complaints. A Sponsor representative must be informed of any product related complaints.

In the Registry adverse events are defined as any unfavorable and unintended sign, or symptom or disease temporally associated with the device. The AEs will be categorized as related to the device (Adverse Device Effect) or not.

In addition all adverse events will be further categorized as serious or not. Serious adverse events (SAEs) are defined as those causing death, fetal distress, fetal death or congenital abnormality or birth defect, or a life-threatening illness or injury that results in permanent disability, requires hospitalization, or prolongs a hospitalization, and/or requires intervention to prevent permanent injury or damage.

All SAEs will be categorized as related to the device (Serious Adverse Device Effect) or not and must be reported to the Sponsor no later than 3 calendar days from the day the site personnel became aware of the event (or as per the investigative site's local requirements, if the requirement is more stringent than those outlined).

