APPENDIX 1: ANTICIPATED ADVERSE EVENT DEFINITIONS (INTERMACS DEFINITIONS)

Major Bleeding

An episode of SUSPECTED INTERNAL OR EXTERNAL BLEEDING that results in one or more of the following:

- a. Death,
- b. Reoperation,
- c. Hospitalization,
- d. Transfusion of red blood cells as follows:

1. If transfusion is selected, then apply the following rules:

During first 7 days Post-implant

1. Adults (≥ 50 kg): ≥ 4 U packed red blood cells (PRBC) within any 24 hour period during first 7 days post-implant.

After 7 days Post-implant

2. Any transfusion of packed red blood cells (PRBC) after 7 days following implant with the investigator recording the number of units given. (Record number of units given per 24 hour period).

Note: Hemorrhagic stroke is considered a neurological event and not as a separate bleeding event.

Cardiac Arrhythmias

Any documented arrhythmia that results in clinical compromise (e.g., diminished VAD flow, oliguria, pre-syncope or syncope) that requires hospitalization or occurs during a hospital stay.

Cardiac arrhythmias are classified as 1 of 2 types:

- 1) Sustained ventricular arrhythmia requiring defibrillation or cardioversion.
- 2) Sustained supraventricular arrhythmia requiring drug treatment or cardioversion.

Pericardial Fluid Collection

Accumulation of fluid or clot in the pericardial space that requires surgical intervention or percutaneous catheter drainage. This event will be subdivided into those with clinical signs of tamponade (e.g. increased central venous pressure and decreased cardiac/VAD output) and those without signs of tamponade.

Device Malfunctions *

Device malfunction denotes a failure of one or more of the components of the MCS system which either directly causes or could potentially induce a state of inadequate circulatory support (low cardiac output state) or death. A failure that was iatrogenic or recipient-induced will be classified as an Iatrogenic/Recipient-Induced Failure.

Device failure should be classified according to which components fails as follows:

- 1) Pump failure (blood contacting components of pump and any motor or other pump actuating mechanism that is housed with the blood contacting components). In the special situation of pump thrombosis, thrombus is documented to be present within the device or its conduits that result in or could potentially induce circulatory failure.
- 2) Non-pump failure (e.g., electric power supply unit, batteries, controller, interconnect cable)

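### The SAE definition in 3.4.1 ties hospitalization and disability to a life-threatening condition, so admissions that are not life-threatening can be graded non-serious

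*Combined protocol and SAP*

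**What the plan says.** Section 3.4.1 sets the grading task: "In addition all adverse events will be further categorized as serious or not". The definition that decides the grade is a single sentence in three parts:

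- It opens with outcomes that clearly stand alone: "Serious adverse events (SAEs) are defined as those causing death, fetal distress, fetal death or congenital abnormality or birth defect".
- It goes on: "or a life-threatening illness or injury that results in permanent disability, requires hospitalization, or prolongs a hospitalization".
- It closes: "and/or requires intervention to prevent permanent injury or damage".

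The next paragraph of 3.4.1 splits SAEs into device-related (Serious Adverse Device Effect) and not. It adds that SAEs "must be reported to the Sponsor no later than 3 calendar days from the day the site personnel became aware of the event", with the exception "or as per the investigative site's local requirements, if the requirement is more stringent than those outlined".

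For events in general, 3.4 says: "Any subject related events (adverse events, reoperations, rehospitalizations, outcomes) should be reported as they occur". No number of days is attached to that instruction. Section 3.4.3 adds that the reasons for rehospitalization are recorded. No other section restates or corrects the SAE criteria.

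**The concern.** The middle part of the sentence reads as one compound criterion: a life-threatening condition that also leads to disability, admission or a longer stay. On that reading, a subject admitted for a driveline infection that never endangers life does not meet the hospitalization criterion. Nor does a life-threatening episode that resolves during an existing stay without lengthening it, without lasting harm and without preventive intervention.

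Three things in the plan depend on the grade:

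- **Counts.** Serious Adverse Device Effects are a subset of SAEs, so an event graded non-serious is lost from both.
- **Speed.** Only SAEs carry the 3-calendar-day limit.
- **Documentation.** Section 6.6 asks for source records of site awareness, and of the investigator's assessment of device relationship, specifically for SAEs.

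Up to 50 centers (2.1) apply this sentence. Section 6.9 describes remote monitoring for timeliness and plausibility, and the documents describe no adjudication that would bring site-level grading into line.

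**Working it through.** The plan states no figure on this point, so the check is a reading of the text.

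**1. What the clause modifies.** The verbs in the middle part are singular (results, requires, prolongs). They agree with illness or injury, not with the plural subject of the sentence (those, meaning the events). Independent criteria would need plural verbs and no relative pronoun. The grammar therefore makes disability, admission and a longer stay conditions on the life-threatening illness or injury.

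**2. Readings a site could adopt.**

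- A: everything after the relative pronoun, including preventive intervention, is tied to the life-threatening condition.
- B: as A, but preventive intervention stands alone.
- C: as A, but life-threatening qualifies only illness, so any injury needing admission counts.
- D: every item stands alone.

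| Event | A | B | C | D |
|---|---|---|---|---|
| Infection needing admission, not life-threatening, no intervention needed to avert permanent damage | No | No | No | Yes |
| Bleed needing admission, not life-threatening | No | Only if treatment is judged to avert permanent injury | Only if classed as an injury | Yes |
| Life-threatening episode during a stay, with no disability, longer stay or preventive intervention | No | No | No | Yes |
| Permanent disability from an illness that is not life-threatening, no preventive intervention | No | No | No | Yes |

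Only D grades all four as serious, and D is the reading that the grammar least supports. B and C each recover some events but not the infection in the first row.

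**3. Whether such events are expected.** Appendix 1 defines Major Bleeding as "An episode of SUSPECTED INTERNAL OR EXTERNAL BLEEDING that results in one or more of the following", and hospitalization is item c of the list that follows, with no requirement that life be threatened. A psychiatric episode can likewise qualify through hospitalization. The registry therefore expects adverse events that are defined by an admission without any reference to danger to life.

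**4. Size.** Let p be the share of adverse-event admissions that are life-threatening. Under reading A, the number left outside the hospitalization criterion, per 100 such admissions, is 100 × (1 − p). The documents give no p, so the values below are assumptions that show the range:

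- p = 20%: 100 × 0.80 = 80
- p = 50%: 100 × 0.50 = 50
- p = 80%: 100 × 0.20 = 20

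The possible range is 0 to 100. Under reading B, some of these events return through the intervention item, by an amount that the documents also do not give.

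**5. What does not depend on the grade.** The endpoints in 2.4.4 include anticipated adverse events, device malfunctions, reoperations and rehospitalizations; none of the listed endpoints uses the serious/non-serious split. Section 3.4.1 classifies all adverse events by device relationship, so a misgraded device-related event remains an Adverse Device Effect and loses only the serious label.

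**The case against.** The strongest reply is that the sentence is ambiguous, not plainly restrictive, and that little is lost in practice. The intervention phrase may stand alone, and life-threatening may attach only to illness. Adverse events and rehospitalizations are reported as they happen whatever their grade, product-related complaints also go to a sponsor representative, and stricter local rules override the 3-day limit. The documents show no actual divergence between sites.

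Much of this stands. The events are not lost from the registry, and divergence between sites is a risk, not an observed fact. But those other routes carry no 3-day limit, and stricter local rules change the timing of reports, not the grade. As the table shows, neither alternative reading restores hospitalization as a criterion. That several readings are open is itself a fault in a definition that many centers must apply alike.

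A reader might also infer that Appendix 1 contradicts 3.4.1, because the same bleed can be major yet not serious. The documents do not support that. Appendix 1 names types of event and 3.4.1 grades seriousness; the two labels are separate and may differ. Appendix 1 shows only that admission-defined events are foreseen.

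**Conclusion.** The point holds as a fault in the definition. Followed as written, 3.4.1 lets an adverse event that requires admission but does not threaten life be graded non-serious. Such an event leaves the SAE count and, if device-related, the Serious Adverse Device Effect count, and it escapes the 3-day report where local rules are no stricter. The same wording does not make a life-threatening event sufficient, and it leaves the standing of the intervention item unclear.

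This rests on a grammatical reading and on the assumption that some adverse-event admissions are not life-threatening. It does not need a particular share.

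Two stronger conclusions should not be drawn. One is that most admissions would be graded non-serious: that requires p below 50%, and the documents give no value. The other is that the registry's adverse-event or rehospitalization rates are distorted: those endpoints do not use seriousness, and the underlying events are still captured. The effect is confined to seriousness grading, the counts built on it, the SAE source documentation and the speed of reporting. It is worth correcting because the remedy is cheap, but no listed endpoint is invalidated.

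**What to change.** Replace the sentence in 3.4.1 with a list and state that any one item is enough:

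- death
- life-threatening illness or injury
- permanent disability
- hospitalization
- prolongation of hospitalization
- intervention to prevent permanent injury or damage
- fetal distress, fetal death, congenital abnormality or birth defect

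For data already collected, use the rehospitalization records and their reasons to flag adverse events graded non-serious that appear to have led to an admission. Query the sites to re-grade those events and document device relationship. Do not reclassify automatically: 3.4.3 shows no formal link between an adverse event and an admission, and 6.6 calls for the investigator's own assessment. This check will not find events that prolonged the index implant stay, and the report should say so.

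The cost is a short amendment to one paragraph, a one-off listing and some query work at sites, in a registry of up to 500 subjects and 50 centers. More 3-day reports will be filed, and the SAE count will rise for reasons of definition, which should be explained wherever counts from before and after the change are shown together.

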3.4.2 Reoperations

Any cardiac or non-cardiac surgical or operative procedures (including pump exchanges/replacements) that occur during the follow-up period will be collected.

3.4.3 Rehospitalizations

Rehospitalizations and the associated reasons will be captured during the follow-up period.

3.4.4 Outcomes

The subjects's outcome during the follow-up period will be captured and should be reported as occurs. The outcomes include: transplanted, explanted, expired, or withdrawn.

The subject retains the right to withdraw from the registry data collection at any time. Should the subjects elect to withdraw from the registry data collection, the reason for withdrawal should be documented.

4 DATA ANALYSIS

The endpoints were selected to evaluate the same parameters as those collected in the HM3 CE Mark Study.

In general, continuous data will be presented as the number of subjects, mean with standard deviation, median and minimum and maximum values. Categorical data will be reported as frequencies and percentages. Survival data will be presented using the Kaplan-Meier product limit method.

Statistical analysis will be performed using SAS version 9.1 or higher.

5 SUBJECT SAFETY

5.1 Risks

This registry will be initiated upon HM3 LVAS commercial approval therefore there is no added procedural risk to subjects participating in this post-market registry. No risk or procedures beyond those required for routine standard of care will be imposed. The data collected for this registry are mostly from medical chart abstraction. The only exception is the collection of functional capacity data and QoL data. These data are standard of care for heart failure subjects receiving VADs and are not considered greater than minimal risk.

There is always the risk of loss of confidentiality. However, safeguards, policies and procedures are in place to keep personal health information confidential. No published or unpublished report or visual or speaking presentation about the study will include any material that will identify a subject participating in this registry.

5.2 Mitigations

As the device will be commercially approved at the initiation of this post-market registry, mitigations and treatment for any adverse events associated with VAD therapy would be per the current practice standards and standards of care as determined by the treating physician.

5.3 Benefits

There is no direct benefit to the heart failure subjects who participate in this post-market registry. However, future heart failure subjects may benefit from the knowledge gained through this registry.

6 ETHICAL REQUIREMENTS

6.1 Informed Consent for Data Collection

Prior to data entry into the registry the subject or legal representative must sign an informed consent. The informed consent must inform the subject that the subject's data will be entered into a database outside of the hospital. The informed consent must have prior approval from the Ethics Committee (EC).

The site is responsible for keeping the original signed informed consent form on file.

6.2 Ethics Committee Review

Before initiation of the registry, EC approval of the protocol and the informed consent form (ICF) must be obtained. Any modifications made to the ICF should be sent to the Sponsor for approval, prior to submitting to the EC. Copies of the EC submission and approval, including the approved informed consent form, should be forwarded to the Sponsor prior to the enrollment of subjects into the registry. Copies of all submissions to and correspondence from the Ethics Committee (approvals and disapprovals) must be maintained on file at the site.

6.3 Data Handling and Record Keeping

Sponsor and/or its affiliates will maintain documentation of the systems and procedures used in data collection for the duration of the clinical investigation.

CRF data collection will be performed through a secure web portal and only authorized personnel will access the Electronic Data Capture (EDC) system using a unique username and password to enter, review or correct data. Passwords and electronic signatures will be strictly confidential.

The data will be subjected to consistency and validation checks within the EDC system and supplemental review by the Sponsor.

At the conclusion of the clinical investigation, completed CRF images with the date-and-time stamped electronic audit trail indicating the user, the data entered, and any reason for change (if applicable) will be provided to the investigational sites.

For the duration of the clinical investigation, the Investigator will maintain complete and accurate documentation including, but not limited to, medical records, clinical investigation progress records, laboratory reports, CRFs, signed ICFs, device accountability records (if applicable), correspondence with the IRB/EC and clinical investigation monitor/Sponsor, adverse event reports, and information regarding subject discontinuation or completion of the clinical investigation.

6.4 Protection of Personally Identifiable Information

The Sponsor respects and protects personally identifiable information collected or maintained for this clinical investigation.

The Sponsor implements technical and physical access controls to ensure that Personal Information is accessible only to and processed only on a 'need to know' basis, including periodic review of access rights, and revocation of access when an individual's employment is terminated or the individual transitions to a role that does not require access to Personal Information, and appropriate restrictions on physical access to premises, facilities, equipment, and records containing Personal Information.

The Sponsor requires the investigational sites to transfer into Sponsor's data management systems only Information (key-coded) necessary to conduct the Clinical Investigation, such as the subject's medical condition, treatment, dates of treatment, etc. The Sponsor discloses as part of the clinical investigation informed consent process that some Sponsor representatives still may see Personal Information at the participating sites for technical support of the participating physicians on the device implant or procedures, monitoring and quality control purposes. Confidentiality of Personal Information will be observed by all parties involved at all times throughout the clinical investigation. The privacy of each subject and confidentiality of his/her information will be preserved in reports and when publishing any data.

The Sponsor data management systems and processes were designed, developed, and tested according to industry standards to appropriately safeguard Confidential Information (including any Personal Information) against unauthorized access and/or interference by third parties, intrusion, theft, destruction, loss or alteration. Clinical Investigation data are encrypted in transit and at rest.

The Sponsor maintains a Privacy Incident procedure that complies in all respects with Applicable Law and industry best practices.

6.5 Data Management Plan

A Data Management Plan (DMP) will describe procedures used for data review, data cleaning, and issuing and resolving data discrepancies. If appropriate, the DMP may be updated throughout the duration of the clinical investigation. All revisions will be tracked and document controlled.

6.6 Source Documentation

Regulations and GCP require the Investigator to maintain information in the subject's original medical records that corroborates data collected on the CRFs. In order to comply with these regulatory requirements/GCP, the following information should be included in the subject record at a minimum and if applicable to the clinical investigation:

- Medical history/physical condition of the subject before involvement in the clinical investigation sufficient to verify CIP entry criteria
- Dated and signed notes on the day of entry into the clinical investigation referencing the Sponsor, CIP number, subject ID number and a statement that informed consent was obtained
- Dated and signed notes from each subject visit (for specific results of procedures and exams)
- Adverse events reported and their resolution, including supporting documents, such as discharge summaries, catheterization laboratory reports, ECGs, and lab results including documentation of site awareness of SAEs and of investigator assessment of device relationship for SAEs.
- Subject's condition upon completion of or withdrawal from the clinical investigation
- Any other data required to substantiate data entered into the CRF
- Subject reported outcome measures may be completed using CRF worksheets. These serve as the source documentation.

6.7 Case Report Form Completion

Primary data collection based on source-documented hospital and/or clinic chart reviews will be performed clearly and accurately by site personnel trained on the CIP and CRF completion. The investigator will ensure accuracy, completeness, legibility and timeliness of the data reported to the Sponsor on the CRFs and in all required reports.

Data on CRFs will be collected for all subjects that are enrolled into the clinical investigation. Only authorized site personnel will be permitted to enter the CRF data through the EDC system deployed by the Sponsor. An electronic audit trail will be used to track any subsequent changes of the entered data.

